## HUMAN SUBJECTS

### Institutional Review Board (IRB) Review and Informed Consent

This protocol and the informed consent document and any subsequent modifications will be reviewed and approved by the University Hospitals Cleveland Medical Center CWRU IRB. A signed informed consent form will be obtained from each study subject. The informed consent form will describe the purpose of the study, the procedures to be followed, and the risks and benefits of participation. A copy of the consent form will be given to the subject, and this fact will be documented in the subject's record.

### Subjects and Data Confidentiality

All laboratory specimens, evaluation forms, reports, and other records that leave the site will be identified by coded number only to maintain subject confidentiality. All records will be kept in a locked file cabinet. All computer entry and networking programs will be done with coded numbers only by study staff. Clinical information will not be released without written permission of the subject, except as necessary for monitoring by the IRB, FDA, or OHRP.

### Recruitment plans

Subjects will be primarily recruited from the practice of the investigator (the Special Immunology Unit at University Hospitals Case Medical Center). All subjects seen at the Special Immunology Unit who meet the inclusion/exclusion criteria will be approached for study participation. In addition, subjects may be referred to the study by their primary care provider or their HIV provider from other HIV practices.

### Study Discontinuation

The study may be discontinued at any time by the IRB as part of its duties to ensure that research subjects are protected.

### **Post-study Follow-up and Transition of Care**

During the study period, the study subject will be encouraged to continue their routine regular follow up with their primary HIV care provider, whether in the Special Immunology Unit or in an outside HIV practice that referred them to the study. The study is not meant to replace the routine HIV care visits. After the study subject completes the study, he/she will continue to be followed by his/her primary HIV provider. There will be no additional follow-up for this study after the 24-week of the pre-defined study period. In addition, after the study subject completes the study, he/she will not be provided any further zinc supplements. If the subject primary care provider decides that it is in the best interest of the patient to be on zinc, he/she would be prescribed such supplements. The decision related to any follow-up or treatment after the study period will be left to the subject and his/her primary care provider.

### **BIOHAZARD CONTAINMENT**

As the transmission of HIV and other blood-borne pathogens can occur through contact with contaminated needles, blood, and blood products, appropriate blood and secretion precautions will be employed by all personnel in the drawing of blood and shipping and handling of all specimens for this study, as currently recommended by the Centers for Disease Control and Prevention and the National Institutes of Health.

All infectious specimens will be packaged and sent in accordance with requirements mandated by the International Air Transport Association Dangerous Goods Regulations- Packing Instruction 602.

### **DATA SAFETY AND MONITORING PLAN**

This is a pilot study that will serve to collect preliminary data on the anti-inflammatory effects of zinc in HIV. However, an independent data and safety monitoring board will be established to include an independent HIV expert, a statistician, and a community advocate. The DSMB will meet every 6 months (or earlier as needed) to review safety data and adverse events. The DSMB will function to: review and approve plans for data and safety monitoring for this trial; to review data on a timely basis and to ensure proper conduct and progress of study; to review credentials of investigator and project staff; to make recommendations to project investigator and staff regarding issues of concern; to address adverse events. The DSMB will meet twice a year in Cleveland, Ohio or by phone conferences to review study protocols progress, and safety data. Meetings will be held in an open format, except if privileged data are discussed. At the time of the continuing review, the DSMB report will be prepared by [name] and her staff and will include enrollment and dropout rates, protocol deviations, subjects symptoms, review of clinical and laboratory results.

The DSMB will review interim data to detect evidence of adverse events to determine if the trial should continue as originally designed, should be changed or even stopped based on the data. The DSMB will evaluate the progress of the trial, including periodic assessments of the recruitment goals, protocol adherence, accrual and retention of participants. The DSMB will protect confidentiality of the study subjects.

The Principal Investigator will report all > Grade 2 adverse effects deemed to be possibly, probably or definitely related to study participation to the University Hospitals Cleveland Medical Center CWRU IRB within one week in writing. All >1 Grade 1 adverse effects deemed to be possibly, probably or definitely related to study participation will be collected. The Principal Investigator, investigators, and study nurse will prepare every year an update to renew the University Hospitals Cleveland Medical Center CWRU IRB approval of the clinical studies. In this renewal, investigators will inform the IRB about adverse effects Grade > 1 noted during the performance of the study. Accrual, retention, and data quality and timeliness will be monitored by the Principal Investigator.

**Protocol Deviations:** All deviations will be documented in the source document and the IRB will review all protocol deviations. Any deviation that may affect study conduct or safety will promptly be reported within 72 hours.

**Quality Control Committee:** Not applicable

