**SECONDARY:**

- Metabolic/CVD factors: endothelial function and insulin resistance

-Safety/tolerability:- Tolerance of zinc reported by patients and safety measures will also be assessed (percent of subjects with >Grade 2 adverse events possibly or probably due to study drugs).

--Markers of gut integrity: intestinal fatty acid binding protein (I-FABP), and zonulin.

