**BACKGROUND:**

It has been estimated by the World Health Organization that nearly two billion subjects may be zinc deficient in the developing countries. This is due to the fact that most of these populations consume mainly bread made of whole wheat flour, which is high in phosphate compound that decreases the absorption of both iron and zinc. The phytate to zinc molar ratio >20 in a diet is unfavorable for zinc absorption and this may lead to zinc deficiency. In the developed countries, zinc deficiency is also prevalent in the elderly population or even in younger subjects with HIV, where up to 30% of non-malnourished subjects were found to be zinc-deficient. Low concentrations of zinc are prevalent in HIV-1-infected male and female drug users as well as other HIV-1-infected cohorts. Such low concentrations of plasma zinc have been linked with disease progression, independent of baseline CD4 cell count, lymphocyte concentrations and age- and calorie-adjusted dietary intake. Of particular importance, low plasma zinc levels have been associated with a threefold increased risk of HIV-1-related death in HIV-1-seropositive drug users.

In mild to moderate deficiency of zinc, the clinical manifestations may include growth retardation in children, rough skin, poor appetite, mental lethargy, delayed wound healing, T cell-mediated immune dysfunction, and neurosensory disorders

Pertinent to this proposal, zinc has anti-inflammatory properties due to NFkB blockade, and is an anti-oxidant agent. Zinc decrease NF- $\kappa$ B activation and its target genes such as TNF- $\alpha$ , IL-1 $\beta$ , and VCAM and increased the gene expression of A20 and PPAR- $\alpha$ , the two zinc finger proteins with anti-inflammatory properties. Thus, zinc decreased the expression of these cytokines and molecules by inhibition of NF- $\kappa$ B activation via A20 and PPAR- $\alpha$  pathways. As such, zinc supplementation has been investigated as immunomodulatory and anti-inflammatory agents

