### **SECONDARY:**

- Metabolic/CVD factors: endothelial function and insulin resistance

-Safety/tolerability:- Tolerance of zinc reported by patients and safety measures will also be assessed (percent of subject with >Grade 2 adverse events possibly or probably due to study drugs).

--Markers of gut integrity: intestinal fatty acid binding protein (I-FABP), and zonulin.

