### **TOXICITY MANAGEMENT**

Only toxicities related to study drugs (zinc) will be considered. Toxicities felt to be unrelated to study drugs will be left to the discretion of the primary care provider of the study participants. AACTG grading system will be used for evaluation for Grading Adult Adverse Experiences.

-Subjects who develop a new Grade 1 adverse event or toxicity may continue study drug without alteration of the dosage. Subjects experiencing Grade 1 adverse event who choose to withdraw from the study should be encouraged to complete the study evaluations as outlined in the Schedule of events.

- For all toxicities of Grade 2 thought to be related to the study drug, the study medication can be held at the discretion of the local investigator. If unable to resume it within 3 weeks, then the subject will be taken off study drugs but will continue to be followed and undergo the evaluations as per schedule of events.

- For all toxicities Grade 3 thought to be related to study drug, study medication will be held until the toxicity grade returns to  $\leq$  Grade 2 or to the entry value. If unable to resume study drugs for longer than 3 weeks, then the subject will be taken off study drugs but will continue to be followed and undergo the evaluations as per schedule of events.

- For any Grade 4 toxicity (confirmed  $\geq$  2 values for laboratory abnormalities) regardless of the cause, subjects will be taken off study drugs but will continue to be followed and undergo the evaluations as per schedule of events. Exceptions are asymptomatic elevation of indirect bilirubin in subjects receiving indinavir or atazanavir therapy, asymptomatic elevation of CPK, or elevations in lipid levels.

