#### **Adverse Event**

An Adverse Event (AE) is the development of an undesirable medical condition or the deterioration of a pre-existing medical condition following or during exposure to a pharmaceutical product, whether or not considered causally related to the product. An undesirable medical condition can be symptoms (eg, nausea, chest pain), signs (eg, tachycardia, enlarged liver) or the abnormal results of an investigation (eg, laboratory findings, ECG). In clinical studies, an AE can include an undesirable medical condition occurring at any time, including run-in or washout periods, even if no study treatment has been administered.

Any detrimental change in a patient's condition subsequent to them entering the study and during the follow-up period should be considered an AE. When there is a deterioration in the condition for which the study treatment is being used, there may be uncertainty as to whether this is lack of efficacy or an AE. In such cases, unless the reporting physician considers that study treatment contributed to the deterioration or local regulations state to the contrary, the deterioration should be considered a lack of efficacy. Signs and symptoms of disease progression are therefore not considered AEs.

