#### **Serious Adverse Event**

- A Serious Adverse Event (SAE) is an AE occurring during any study phase (eg, run-in, treatment, washout, follow-up), and at any dose of the investigational product, comparator or placebo, that fulfills one or more of the following criteria:

- Results in death
- Is immediately life-threatening
- Requires inpatient hospitalization or prolongation of existing hospitalization
- Results in persistent or significant disability or incapacity
- Is a congenital abnormality or birth defect
- Is an important medical event that may jeopardize the patient or may require medical intervention to prevent one of the outcomes listed above.

Any event or hospitalization that is unequivocally due to progression of disease, as determined by the investigator, must not be reported as an SAE.

The causality of SAEs (their relationship to all study treatment) will be assessed by the investigator(s)

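### Safety is part of the primary objective, but the only safety measure with a defined statistic counts related events above Grade 2, and the sections disagree on which adverse events are recorded

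*Combined protocol and SAP*

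**What the plan says.** Safety appears in the primary objective, in both the Précis and the body, and again in the Hypothesis. As a measured quantity it is a secondary endpoint: in the Précis, the "percent of subjects with >Grade 2 adverse events possibly or probably due to study drugs", with the same threshold in the body Study Endpoints ("percent of subject with >Grade 2 adverse events"). The same endpoint line also says that patients' reported tolerance of zinc will be assessed, without saying how.

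On what is recorded, the sections differ:
- The Adverse Event section defines an event "whether or not considered causally related to the product".
- The Data Safety and Monitoring Plan says: "All >1 Grade 1 adverse effects deemed to be possibly, probably or definitely related to study participation will be collected". The same section has the annual IRB renewal report effects above Grade 1 seen during the study, with no condition on relatedness.
- Toxicity Management opens with "Only toxicities related to study drugs (zinc) will be considered" and then makes an exception for Grade 4, which is acted on whatever the cause.
- The visit procedures for weeks 6, 12, 18 and 24 include questionnaires on symptoms and changes in health, given to everyone.

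On Grade 2, Toxicity Management says: "For all toxicities of Grade 2 thought to be related to the study drug, the study medication can be held", at the local investigator's discretion. If drug cannot be resumed within 3 weeks, the participant comes off it and stays in follow-up.

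The Statistical Considerations describe no safety analysis.

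**The concern.** A randomised, blinded placebo arm lets the trial compare adverse events between arms without anyone having to judge causation. An endpoint restricted to events judged related gives that advantage up, and a floor above Grade 2 restricts it to severe events.

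The effects named in the Rationale and in Risks and Discomforts are nausea, vomiting and abdominal pain. When these occur at Grade 1 or 2 they do not enter the percentage, even if they end treatment. A report could then give a zero, or close to it, as evidence for the safety part of the primary objective while the arms differ in tolerability or in stopping drug.

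The inconsistent recording rules add a practical risk. Staff who follow the collection sentence would keep fewer events than staff who follow the definition, and an all-cause table could not be rebuilt reliably afterwards.

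**Working it through.** The plan states no adverse event rate, safety sample size or safety power, so there is no figure of its own to reproduce. The check has two parts.

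**1. What the counted percentage includes**

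| Event | Rule elsewhere in the plan | In the percentage? |
|---|---|---|
| Grade 1, any cause | Drug may continue (Toxicity Management) | No |
| Grade 2, related, drug held and not resumed within 3 weeks | Off drug, followed up | No |
| Grade 3 or 4, possibly or probably related | Held, or off drug | Yes |
| Grade 3 or 4, definitely related | Named in the Data Safety and Monitoring Plan | Not on a literal reading |
| Grade 3, judged unrelated | An adverse event by definition | No |
| Grade 4, judged unrelated | Off drug whatever the cause, with listed exceptions | No |

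The reference for relatedness also differs: the study drugs in the endpoint, study participation in the collection sentence. No endpoint counts holds or discontinuations.

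The grade floor in the collection sentence can be read as above Grade 1 or as Grade 1 and up. On either reading related Grade 2 effects are collected. What is in doubt is related Grade 1 effects and anything judged unrelated.

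**2. What a zero would mean (illustration, all event rates assumed)**

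Input: 62 zinc participants (Study Design; Sample Size and Power Analysis). The Précis gives 63.

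Chance that the count is zero in the zinc arm = (1 − p)^62, where p is the true rate of counted events:
- p = 0.5%: 0.995^62 = 0.733
- p = 1%: 0.99^62 = 0.536
- p = 2%: 0.98^62 = 0.286
- p = 5%: 0.95^62 = 0.042

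With 63 participants the 1% case is 0.99^63 = 0.53, so the choice of arm size hardly matters.

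One-sided 95% upper limit after 0 of 62: 1 − 0.05^(1/62) = 4.7%. This limit applies to related events above Grade 2 only. It says nothing about Grade 1 or 2 events or about stopping drug.

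**Arm comparison**, 31 placebo and 62 zinc, one-sided 0.10 (the plan's general test level; none is stated for safety). Normal approximation: power = Φ[(d − 1.2816 × se0)/se1], with d the difference in rates, se0 the pooled and se1 the unpooled standard error.
- 2% vs 5%: pooled rate (31 × 0.02 + 62 × 0.05)/93 = 0.04; se0 = 0.0431; se1 = 0.0374; Φ[(0.03 − 0.0552)/0.0374] = Φ(−0.675) = 25%.
- 5% vs 20%: pooled rate (31 × 0.05 + 62 × 0.20)/93 = 0.15; se0 = 0.0785; se1 = 0.0641; Φ[(0.15 − 0.1007)/0.0641] = Φ(0.769) = 78%.
- By the same formula, 1% vs 3% gives 21%, 5% vs 15% gives 56% and 5% vs 25% gives 91%.

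The approximation is generous when events are few. Summing the binomial probabilities of every table with a one-sided Fisher p-value of at most 0.10 gives 5% power for 2% vs 5% and 70% for 5% vs 20%. The two cases assume different gaps between arms, so they are not a like-for-like gain. They show that a comparison limited to rare severe events has little power at this size, while one that includes Grade 2 could detect a large difference.

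**The case against.** The strongest defence is that the plan gathers more than its endpoint counts. Four visits carry unfiltered symptom questionnaires, and the Rationale describes blood monitoring every 6 weeks. The DSMB report covers symptoms, laboratory results and dropout. The annual IRB update has no relatedness filter, and participants off drug are still followed. A threshold of related events above Grade 2 is also a stated choice in a trial that calls itself a pilot and has an independent DSMB.

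Much of this stands, and it rules out several stronger readings that a reader might infer:
- *That lower-grade effects leave no trace.* Patient-reported tolerance is in the same endpoint, and related Grade 2 effects are collected. They are outside the one quantified measure.
- *That events are collected only if judged related.* One sentence says so, and other sections do not. The sentence "Only toxicities related to study drugs (zinc) will be considered" sits under toxicity management and does not set what is recorded. The finding is a contradiction to reconcile.
- *That an all-cause comparison is impossible.* Unfiltered symptom data will exist. What is missing is a plan to grade and tabulate them by arm.
- *That frequent mild-to-moderate intolerance is expected.* The protocol calls the named effects uncommon and gives no grade.
- *That the disease-progression wording hides harm from zinc.* The plan does say "Any event or hospitalization that is unequivocally due to progression of disease, as determined by the investigator, must not be reported as an SAE". That covers only unequivocal cases, and the Adverse Event section keeps a deterioration as an adverse event if the physician thinks treatment contributed. The Background statement "Such low concentrations of plasma zinc have been linked with disease progression" concerns low zinc and gives no reason to expect harm from supplementation. HIV-1 RNA and CD4 are also taken from the chart during follow-up. This wording is not part of the point.

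The defence does not supply a metric for tolerance, a by-arm summary of all-cause events or discontinuations, or a single rule for what is recorded.

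**Conclusion.** The concern holds in this limited form. On the text alone, the only quantified safety measure leaves out Grade 1 and 2 events, Grade 2 discontinuations, events judged unrelated and, literally, definitely related events. The collection sentence conflicts with the definition of an adverse event and with the annual IRB update. These statements need no assumption.

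The size does rest on assumption. At assumed true rates of 0.5% to 5% for related events above Grade 2, the zinc count is zero in 73% down to 4% of trials with 62 participants. A zero is therefore weak support for a claim of safety at the lower rates, and at any rate it does not address tolerability. The documents do not say which rate applies.

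This is an inexpensive improvement to a safety plan that is incomplete and inconsistent. It does not affect the zinc-level or biomarker analyses.

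**What to change.** 1. **Data Safety and Monitoring Plan.** Replace the collection sentence with a rule that all adverse events of every grade are recorded from randomisation, regardless of attribution, with grade and relatedness as recorded fields. This removes the garbled grade floor and agrees with the Adverse Event definition.
2. **Study Endpoints (Précis and body).** Add, by arm, the percentage with any Grade 2 or higher adverse event regardless of attribution, and the percentage who stop study drug because of an adverse event. The second gives tolerability a defined measure.
3. **Same place.** Keep the percentage with related events above Grade 2 as supportive, and add *definitely* to its wording so that it matches the Data Safety and Monitoring Plan.
4. **Toxicity Management.** Leave its rules as they are; nothing here bears on them.

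The cost is more adverse event lines to record and grade, largely from questionnaires already given at weeks 6, 12, 18 and 24, with no new visits. The downside is more background events in both arms, which adds noise to the all-cause percentages and is the reason to keep the related count beside them.

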### **Adverse Events**

#### **Definitions**

The definitions of Adverse Events (AEs) and Serious Adverse Events (SAEs) are given below. It is of the utmost importance that all staff involved in the study be familiar with the content of this section. The principal investigator is responsible for ensuring this.

#### **Adverse Event**

An Adverse Event (AE) is the development of an undesirable medical condition or the deterioration of a pre-existing medical condition following or during exposure to a pharmaceutical product, whether or not considered causally related to the product. An undesirable medical condition can be symptoms (eg, nausea, chest pain), signs (eg, tachycardia, enlarged liver) or the abnormal results of an investigation (eg, laboratory findings, ECG). In clinical studies, an AE can include an undesirable medical condition occurring at any time, including run-in or washout periods, even if no study treatment has been administered.

Any detrimental change in a patient's condition subsequent to them entering the study and during the follow-up period should be considered an AE. When there is a deterioration in the condition for which the study treatment is being used, there may be uncertainty as to whether this is lack of efficacy or an AE. In such cases, unless the reporting physician considers that study treatment contributed to the deterioration or local regulations state to the contrary, the deterioration should be considered a lack of efficacy. Signs and symptoms of disease progression are therefore not considered AEs.

